8.2.2. Supportive Analyses of Primary and Secondary Immunogenicity Endpoints

8.2.2.1. Supportive Analyses of Estimand 2

To assess the magnitudes of the differences between the treatment groups (ARCT-021 vs. Placebo) in SARS-CoV-2 neutralizing antibody (NAbs) and SARS-CoV-2 binding antibody (BAbs) endpoints, an analysis of covariance (ANCOVA) model will be fitted to the natural log transformed neutralizing antibody titers measured against SARS CoV 2 with terms for treatment group, age group (≥ 18 to < 56 and ≥ 56 years) (stratification factor at randomization) and natural log baseline titer by each post-vaccination immunogenicity visit. No imputation of missing data will be done.

The geometric least squares mean (GLSM) and corresponding 2-sided 95% CI for the antibody titers for each treatment group will be provided by visit. The GLSM and corresponding 95% CI results in log-transformed scale estimated from the model will be back-transformed to obtain these estimates in the original scale. Geometric mean ratio (GMR), estimated by the ratio of GLSM and the corresponding 2-sided 95% CI will be provided to assess the treatment difference between ARCT-021 group vs. placebo group at each visit.

ANCOVA analyses will be performed for the priming vaccination period on mITT analysis set only.

8.2.2.2. Supportive Analyses of Estimand 3

The common difference of seropositivity and seroconversion rates and 95% CIs between each vaccine dose group and the placebo will be estimated using the Miettinen-Nurminen method with age group (≥ 18 to < 56 and ≥ 56 years) as stratification factor for each time point.

Miettinen-Nurminen analyses will be performed for the priming vaccination period on mITT analysis set only.

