2.1. Primary Objectives and Endpoints

The primary objectives and endpoints are presented in Table 2-1 (For estimands, see [Appendix 3](#)).

Table 2-1 Primary Objectives and Endpoints

Objective(s)	Endpoint Descriptions
Primary	
• To assess the safety and reactogenicity of ARCT-021 compared to placebo for priming vaccination	Safety will be evaluated in all participants receiving at least 1 administration of study vaccine (ARCT-021 or placebo) and will be summarized for each vaccination as number and percentage of participants with: 
• Any unsolicited adverse event (AE) initiating within 28 days after each study vaccine administration, by severity and relationship to study vaccine• Any medically attended adverse event (MAAE), new onset of chronic disease (NOCD), AE leading to discontinuation/withdrawal or serious adverse event (SAE) through Early Termination• Safety laboratory assessment before and 7 days after each study vaccine administration, by toxicity grade Reactogenicity will be evaluated in all participants receiving at least a single administration of study vaccine and will be summarized for each vaccination as number and percentage of participants with: Any solicited local or systemic AE initiating within 7 days after each study vaccine administration, by toxicity grade

 To assess the neutralizing antibody responses of ARCT-021 compared to placebo for priming vaccination 	
Neutralizing antibody (NAb) responses will be evaluated in all participants receiving at least 1 administration of study vaccine (ARCT-021 or placebo).
 
 Geometric Mean Titer (GMT) measured at all time points Geometric Mean Fold-rise from baseline (GMFR); measured at all time points after baseline (= Day 0) Percentages of participants with ≥ 2- and 4-fold increase in titer from baseline (Seroconversion [SC]); measured at all time points after baseline GMT ratio (ARCT-021/placebo) measured at all time points

 To select the dose and schedule for use in the Phase 3 study in adult participants 	
Safety and reactogenicity data after each priming vaccine administration and immunogenicity response measured 28 days after each priming vaccination will be evaluated in younger (18 to < 56 years) and older (≥ 56 years) adults

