All CIs will be 2-sided and performed using a 5% significance level. No multiplicity adjustment will be made for this study where multiple treatment groups and endpoints are being evaluated.

All analyses adjusting for age group (≥ 18 to <56 years; ≥ 56 years) will use the values derived from age reported in the interactive response technology (IRT) which was used for randomization stratification.

Early termination visits will be summarized separately for the priming vaccination period and the booster vaccination period, respectively.

Analysis will be presented by study phase and study treatment group where applicable as per [Table 4-1](#) below:

Table 4-1 **Study Phase and Study Treatment Groups**

Study Phase	Study Treatment Groups	Shell Presentation of Treatment Group
Priming Vaccination	ARCT-021 7.5 µg - Placebo	A
	ARCT-021 5.0 µg - ARCT-021 5.0 µg	B
	ARCT-021 7.5 µg - ARCT-021 7.5 µg	C
	Placebo	D
Booster Vaccination	ARCT Priming - ARCT-021 Booster	E1
	Placebo Priming - ARCT-021 Booster	E2
	ARCT Priming - ARCT-154 Booster	F1
	Placebo Priming - ARCT-154 Booster	F2
	ARCT Priming - ARCT-165 Booster	G1
	Placebo Priming - ARCT-165 Booster	G2
	ARCT Priming - Placebo/No Booster	H1
	Placebo Priming - No Booster	H2
Priming Vaccination (Re-enrolled Subjects Only)	ARCT-021 7.5 µg - Placebo	A
	ARCT-021 5.0 µg - ARCT-021 5.0 µg	B
	ARCT-021 7.5 µg - ARCT-021 7.5 µg	C

For some summary tables of booster vaccination period, active boosters will be pooled, and treatment groups will be presented like the following:

Booster Vaccination	ARCT-021 7.5 µg - Placebo - ARCT Booster	A1
	ARCT-021 7.5 µg - Placebo - Placebo Booster/ No Booster	A2
	ARCT-021 5.0 µg - ARCT-021 5.0 µg - ARCT Booster	B1
	ARCT-021 5.0 µg - ARCT-021 5.0 µg - Placebo Booster/No Booster	B2
	ARCT-021 7.5 µg - ARCT-021 7.5 µg - ARCT Booster	C1
	ARCT-021 7.5 µg - ARCT-021 7.5 µg - Placebo Booster/No Booster	C2
	Placebo - ARCT Booster	D1
	Placebo - No Booster	D2

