4.6. Missing Data Handling and Imputation Rules

No missing safety and reactogenicity results will be imputed. Incomplete AE onset and end dates will be imputed according to the rules specified in [Appendix 2](#). For safety analysis, percentages will be based on the analysis set of interest (e.g., Safety Set) within each treatment group and overall for the relevant vaccination/period of interest. For reactogenicity analysis, the denominator will be number of participants in the reactogenicity analysis set for the relevant vaccination/period of interest.

Any immunogenicity results that are below the limit of detection (LOD) or lower limit of quantification (LLOQ) will be imputed as half of the corresponding limit and results above the upper limit of quantification will be imputed as that limit for analysis purposes.

5. Participant Disposition and Protocol Deviations

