
- Seropositivity is defined as any detectable antibody level above the lower limit of quantification (LLOQ) for the specific assay and antibody measured.
- For the MesoScaleDiscovery nucleocapsid antibody test (VAC72_ECL_CoV-2_N), seroconversion will be assessed in 2 ways:
 - Defined as a 2- or 4-fold increase above baseline (pre-vaccination antibody levels).
 - Based on detection of an antibody level ≥ 5000 AU/mL, a threshold associated with evidence of SARS-CoV-2 clinical infection/viral exposure.
- For all other assays and antibodies, seroconversion will be defined as a 2- or 4-fold increase above baseline (pre-vaccination antibody levels).
- For seronegative individuals, one half of the value of the LLOQ will be calculated as the baseline antibody level

The LLOQs for each assay are shown below.

- VAC62_MN_CoV-2 (IU/mL): 7.8431372549
- VAC72_ECL_CoV-2_N (BAU/mL): 0.06372
- VAC72_ECL_CoV-2_RBD (BAU/mL): 0.5168

VAC72_ECL_CoV-2_S (BAU/mL): 0.20723 The GMT will be calculated using the following formula:

$$GMT = e^{\left\{ \frac{\sum_{i=1}^n \log_e(t_i)}{n} \right\}}$$

where t_1, t_2, \dots, t_n are observed immunogenicity titers for n participants.

The GMFR measures the changes in immunogenicity titers within participants. The GMFR will be calculated using the following formula:

$$GMFR = e^{\left\{ \frac{\sum_{i=1}^n \log_e \frac{v_{ij}}{v_{ik}}}{n} \right\}} = e^{\left\{ \frac{\sum_{i=1}^n (\log_e v_{ij} - \log_e v_{ik})}{n} \right\}}$$

where, for n participants, v_{ij} and v_{ik} are observed immunogenicity titers for participant i at time points j and $k=0$ (Baseline, Day 0).

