Estimand Label	Estimand 2 (Geometric Mean Titers/Concentrations)
Estimand Description	
The GMT of NAbs (primary) and BAbs (secondary) against SARS-CoV-2 up to Early Termination after first vaccination with ARCT-021 of each group (5.0, 7.5 µg, or placebo) and with/without booster dose in healthy adults.
 
Interest will lie in comparing the GMT of each dosing regimen to placebo based on the Geometric Mean Ratio (GMR).
 
The hypothetical strategy is used to estimate antibody levels had all scheduled vaccinations been received, and without subsequent SARS-CoV-2 infection or influence from immune-modifying drugs or non-study vaccines. The principal stratum strategy excludes those with active or early SARS-CoV-2 infection within 7 days after the first study vaccine administration.

Analysis Population	Vaccinated healthy adults (as defined by eligibility criteria) without active or early SARS-CoV-2 infection (infection within 7 days after the first vaccination).
Endpoint	Total NAbs (primary) and BAbs (secondary) specific for the SARS-CoV-2 measured pre- and post-priming vaccine administration (on Day 0, 14, 28, 42, 56, and 208) and following booster vaccine administration (Day 236, Early Termination).
Treatment Conditions	Placebo or 5.0 µg or 7.5 µg ARCT-021 administered on Day 0, Day 28; placebo, ARCT-021, ARCT-154, or ARCT-165 administered on Day 208.
Population-Level Summary	The GMT and GMR of comparisons of interest at each time point. GMR will compare responses in placebo-, ARCT-021-, ARCT-154-, and ARCT-165-vaccinated groups at relevant timepoints. For additional considerations on population-level summary see the SAP.
Intercurrent Event Strategy	
IcEv1 (Death)	Hypothetical strategy
IcEv2 (Missed dose)	Hypothetical strategy
IcEv3 (Immune-modifying)	Hypothetical strategy
IcEv4 (Early infection)	Principal stratum strategy (based on study phase)
IcEv5 (Study infection)	Hypothetical strategy
Rationale for Strategies	Hypothetical strategy is used to understand antibody levels achieved through receiving scheduled vaccination, without subsequent SARS-CoV-2 infection and without any influence from immune-modifying drugs or non-study vaccines. In estimation, the hypothetical uses a statistical model on the mITT (excluding data points following intercurrent events and not complete removal of all data for the participant).

Estimand Label	Estimand 3 (Rise/Seroconversion)

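### The per-visit ANCOVA allows no unequal variances, although the plan's own rules push placebo neutralizing titres toward one value: GMR intervals up to 22% too wide and supportive vaccine-group intervals covering as little as 91% at equal group sizes

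*SAP*

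**What the plan says.** SAP 8.2.2.1 fits a separate model at each post-vaccination visit of the priming period: "an analysis of covariance (ANCOVA) model will be fitted to the natural log transformed neutralizing antibody titers measured against SARS CoV 2", with treatment group, age group and log baseline titre as terms. Two results come out of it. "The geometric least squares mean (GLSM) and corresponding 2-sided 95% CI for the antibody titers for each treatment group will be provided by visit", and the GMR is the ratio of those GLSMs with its own 95% interval. Protocol 7.6.4.1 describes the same model. Neither document mentions a group-specific variance or a robust standard error.

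The model is labelled supportive, but it is the only stated source of the GMR. SAP 2.1 lists that quantity among the primary neutralizing-antibody endpoints: "GMT ratio (ARCT-021/placebo) measured at all time points".

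Three data rules bear on the placebo group:

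- SAP 4.6: a result under the detection or quantification limit "will be imputed as half of the corresponding limit".
- SAP 8.2.1: "For seronegative individuals, one half of the value of the LLOQ will be calculated as the baseline antibody level". The LLOQ of the neutralizing assay is 7.843 IU/mL.
- SAP Appendix 3, Tables 13-3 and 13-5: participants with early or baseline infection are excluded. Data after a study infection or a non-study vaccine are dropped by "excluding data points following intercurrent events and not complete removal of all data for the participant".

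The only SD in either document is a common 1.2 on the natural-log scale (Protocol 7.3, SAP 4.2). The main GMT and GMFR intervals in SAP 8.2.1 use the t-distribution on the log values and do not come from the ANCOVA.

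**The concern.** Participants who are uninfected and have had no other COVID-19 vaccine should have little or no neutralizing antibody. Eligibility (Protocol 4.1.2) and the exclusions above aim to leave only such people in the placebo group, and each result below the LLOQ is then replaced by the same number. The placebo group may therefore have very little spread, while the vaccine groups vary.

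An ordinary ANCOVA averages these variances and applies the average to every group. That average is too small for a vaccine group, so its GLSM interval is too narrow. It is too large for the vaccine-minus-placebo difference, so the GMR interval is too wide. Protocol 7.2 plans no hypothesis tests and puts the emphasis on estimation with 95% intervals, so interval accuracy is what this model has to deliver.

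**Working it through.** **The plan's own figures.** SD 1.2 corresponds to a geometric CV of sqrt(exp(1.44) − 1) = 1.79, which agrees with the stated 180%. The stated power above 99% for a 2-fold difference at 75:75 does not follow from that SD: 0.693/(1.2 × sqrt(2/75)) = 3.54, and Φ(3.54 − 1.96) = 94.3% two-sided. At 150:150 it is 99.9%. This is a separate matter and does not affect what follows.

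**Inputs.** Four groups randomized 1:1:1:1, with 75 per group per age cohort, so 150 per group (SAP 4.2). Two-sided 95% intervals (SAP 4). Vaccine SD s = 1.2 (SAP 4.2). Assumed, because not given: r, the placebo SD divided by the vaccine SD; equal SDs in the three vaccine groups; and k, the placebo n divided by the n of one vaccine group. Small effects of the age and baseline terms are ignored.

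**Formulas.**

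- Pooled variance = s²(3 + k·r²)/(3 + k)
- Coverage of a vaccine GLSM interval = 2Φ(1.96 × pooled SD/s) − 1
- GMR width ratio, model over correct, log scale = sqrt[(pooled variance/s²)(1 + 1/k)/(1 + r²/k)]

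**Limiting case, r = 0 and k = 1.** Pooled variance = 0.75s², so pooled SD = 0.866s = 1.039.

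- GLSM coverage = 2Φ(1.96 × 0.866) − 1 = 91.0%
- GMR width ratio = sqrt(0.75 × 2) = 1.225, with coverage 2Φ(1.96 × 1.225) − 1 = 98.4%

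**Range at equal n (k = 1).**

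| Placebo SD / vaccine SD | Vaccine GLSM coverage | GMR interval excess width |
|---|---|---|
| 0 | 91.0% | 22% |
| 0.3 | 91.5% | 19% |
| 0.5 | 92.3% | 14% |
| 0.75 | 93.6% | 7% |
| 1.0 | 95.0% | 0% |

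**A few measurable placebo titres.** Suppose 10% of placebo values lie at 8 times LLOQ/2 and the rest at LLOQ/2. The placebo SD is then ln 8 × sqrt(0.1 × 0.9) = 0.62, so r = 0.52. Coverage is 92.4% and the excess about 13%.

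**Day 208.** Only placebo participants may re-enrol (SAP 3.1), so k can fall below 1; the number is not given. If k = 0.5 and r = 0, pooled variance = (3/3.5)s². GLSM coverage is 93.0%, and the GMR width ratio is sqrt(0.857 × 3) = 1.60, about 60% too wide. With k = 0.5 and r = 0.5 the excess is 34%.

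**Simulation.** A four-group linear model with age, 4,000 runs and r = 0, gave GLSM coverage of 90.6% (n = 75 per group) and 90.7% (n = 150). GMR coverage was 98.4%, and the GMR intervals were 21% and 22% too wide. Welch intervals for the same contrast covered 94.8% and 95.2%.

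**On the ratio scale**, with n = 150 per group, s = 1.2 and r = 0:

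- The GMR limits are the estimate multiplied and divided by exp(1.96 × 1.039 × sqrt(2/150)) = 1.265 under pooling, against exp(1.96 × 1.2/sqrt(150)) = 1.212 with separate variances.
- The vaccine GLSM factor is 1.181 under pooling, against 1.212.

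**The case against.** The strongest reply is that the size of the problem is unknown and its effect is mild. The 91% and 22% figures need a placebo SD of exactly 0, equal vaccine SDs and equal group sizes, and none of these is given for the analysis data. At the one common SD that the documents state, there is no error. The LLOQ/2 rule replaces only results that are below the limit. The antibody criteria for infection act only at a nucleocapsid level of 5000 AU/mL or more (SAP 6.1, Table 13-3), so some undiagnosed infections could stay in the placebo group with measurable titres. The GMR error is conservative and feeds no test or success threshold: for an illustrative GMR of 10 at 150 per group, the interval is 7.9 to 12.7 instead of 8.3 to 12.1. All of this stands, and it is why the size is given as a range.

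A reader might infer more than the documents support:

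- *That the rules fix every placebo value at LLOQ/2.* They push values that way, but no passage says that all placebo results are below the limit.
- *That all vaccine-group intervals under-cover.* Only the supportive GLSM intervals do. The main GMT and GMFR intervals in SAP 8.2.1 are computed from the log values directly.
- *That choosing between schedules is compromised.* No ANCOVA contrast between regimens is planned, and the Phase 3 dose had been chosen by protocol version 4.0 (Protocol Synopsis, Interim Analyses; 7.8).
- *That binding antibodies are equally affected.* The same model is used for them, but nothing shows that placebo binding results collapse to one value.

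What the reply does not remove is that the only planned model for a listed primary endpoint relies on equal variances, and the plan's own data rules make that unlikely for neutralizing antibody.

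**Conclusion.** The point holds as a matter of specification, with a conditional size. Because SAP 8.2.2.1 states no variance structure, the ordinary reading is one pooled residual variance. At equal n and equal vaccine SDs, this puts coverage of the supportive vaccine GLSM intervals between 91% and 95%, and makes the GMR intervals 0% to 22% too wide on the log scale. The extremes correspond to a placebo SD of 0 and a placebo SD equal to the vaccine SD. The data rules make the low end of the SD ratio plausible for neutralizing antibody but do not establish it. At Day 208 the GMR excess could exceed 22% if the placebo group has shrunk and its spread is small; the 60% figure rests on an assumed halving and a placebo SD of 0. The consequence is imprecise reporting of a primary endpoint, not a wrong decision.

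**What to change.** Keep the model terms as they are, and add one sentence to SAP 8.2.2.1: the GLSM and GMR intervals use heteroscedasticity-consistent standard errors (for example HC3) at every visit and in every subgroup ANCOVA. It should be the single prespecified method. A separate residual variance per treatment group is the more familiar option, but it cannot be estimated when every placebo value at a visit is identical, and it would then force a data-dependent switch of method. Robust standard errors still work in that case.

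The change also fits the sponsor's own reasoning: SAP 11 replaces the CMH method with Miettinen-Nurminen on grounds of better coverage.

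The cost is one model option and one sentence. Vaccine GLSM intervals become up to about 15% wider on the log scale (1/0.866 = 1.155), which is the width they should have. If the variances turn out equal, almost nothing is lost.

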8.2.2.3. Other Supportive Analyses

Subgroup analyses will be performed by gender, age group (≥ 18 to < 56 years; ≥ 56 years), and country (US versus Singapore) for selected analyses as noted in Section 8.4. Age group will not be included in the model for ANCOVA analyses by age group. Subgroup analyses will be performed by " ≥ 18 to < 65 years vs. ≥ 65 years" age groups for selected analyses as noted in Section 8.4.

Box plots of titers and fold rise as well as plots of reverse cumulative distribution curves will be provided for each assay by treatment and by each of the subgroups as noted in Section 8.4.

A scatterplot for each of the SARS-CoV-2 binding antibodies and the neutralizing antibody levels at Day 56 will also be produced, both overall and by the subgroups as noted in Section 8.4.

8.3. Exploratory Immunogenicity Analyses

8.3.1. Assays for Response to SARS-CoV-2 Variants

To address the exploratory immunogenicity objective to evaluate responses to SARS-CoV-2 variants, the binding antibody responses of ARCT-021/ARCT-154/ARCT-165 will be compared to placebo for the booster vaccination period. SARS-CoV-2 binding antibodies (BAbs) will be tested using an MSD multiplex assay which measures total immunoglobulin G (IgG) against the full-length spike, RBD and N antigens of the beta strain. Neutralizing antibodies against the beta strain of SARS-CoV-2 will also be measured:

- IgG measured against the Nucleocapsid (N) antigen of the beta variant (B1.351) of SARS-CoV-2 (VAC83_ECL_CoV-2_N)
- IgG measured against the RBD antigen of the beta variant (B1.351) of SARS-CoV-2 (VAC83_ECL_CoV-2_RBD)

- IgG measured against the Spike antigen of the beta variant (B.1.351) of SARS-CoV-2 (VAC83_ECL-CoV-2_S_B.1.351)
- Microneutralization antibody concentration against the beta variant (B.1.351) of SARS-CoV-2 (VAC85_MN_CoV-2)

Similar estimands will be used as for the secondary objective.

The LLOQ for each assay is shown below:

- VAC83_ECL_CoV-2_N (AU/mL; 1:500 dilution): 27
- VAC83_ECL_CoV-2_RBD (AU/mL; 1:500 dilution): 19
- VAC83_ECL_CoV-2_S_B.1.351 (AU/mL; 1:500 dilution): 18
- VAC85_MN_CoV-2 (AU/mL; 1:5 dilution): 14

Assays for other variants may be analyzed as available as part of the exploratory analysis.

8.3.2. CMI Analysis

CMI responses will be evaluated for CMI subset using parametric flow cytometry for quantification and phenotyping and cytokine staining for TNF- α , IL-2, IFN- γ , IL-4, and IL-13. Blood sampling will be performed at Days 0, 14, 28, 42, 56, 208, 215, 236, and Early Termination in participants enrolled at centers identified with capabilities for isolation of peripheral blood mononuclear cells (PBMCs). CMI testing will not be performed on participants re-enrolling at Day 98-198 (i.e., placebo participants who re-enter the study to receive ARCT-021 priming vaccinations).

Descriptive statistics (N, mean, SD, min, Q1, median, Q3, max) will be provided for each visit including change from baseline at each timepoint, where CMI results are available for the priming vaccination period (mITT and PP analysis CMI subsets) and booster vaccination period (Booster mITT CMI subset). When summarizing the Early Termination visit, only include observations within the booster vaccination period post day 236. The following CMI responses will be summarized:

- CD4+ T-cell responses background subtracted (combined pools): IFN- γ , TNF- α , IL-2, IFN- γ + TNF- α +, IFN- γ + TNF- α + IL-2+
- CD8+ T-cell responses background subtracted (combined pools): IFN- γ , TNF- α , IL-2, IFN- γ + TNF- α +, IFN- γ + TNF- α + IL-2+

- Th1/Th2 CD4+ T-cell responses background subtracted (combined pools): IFN- γ , IL-4, IL-4+ IL-13+, IFN- γ + / IL4+ IL13+

Box plots will be provided for the following for priming vaccination period (mITT CMI subset): CD4+/CD8+ IFN γ , IL4+IL13+, IFN γ +/IL4+IL13+, Th1/Th2.

Analyses will be performed overall and by age group (younger adults (≥ 18 - < 56 years), older adults (≥ 56 years)) for priming vaccination period (mITT CMI subset).

Summary tables and figures will exclude any data points collected at or after the first occurrence of the following intercurrent events: death, missed second ARCT-021 (if applicable) dose, use of immune-modifying drugs, and study infection. Summary tables and figures will exclude all data from subjects with early (before Day 7), active or prior SARS-CoV-2 infection at first vaccination.

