Lymphopenia and Neutropenia	
 There are no specific mitigations as these events are not preventable. However, events of lymphopenia and neutropenia observed in the first in human study ARCT-021 were transient and resolved spontaneously. Hematology (CBC) safety laboratory values will be collected and monitored in ARCT-021-04 Study.
Vaccine-Associated Enhanced Respiratory Disease (VAERD) if Subsequently Infected with SARS-CoV-2	
 Vaccination of mice with ARCT-021 produced robust neutralizing antibody response, CD8+T cell response and a balanced, Th1dominant, Th1/Th2 response across all doses (De Alwis 2020) In a SARS-CoV-2 challenge study in a mouse model carrying the human ACE-2 receptor (huACE-2 transgenic mouse), a single dose of ARCT-021 at 2 µg or 10 µg completely protected mice from lung disease and death following challenge with a lethal dose of SARS-CoV-2 (De Alwis 2020) A Th1-dominant CD4+ response was observed on ICS evaluation of subjects at the interim analysis of first-in-human study ARCT-021-01 Eligibility criteria for early phase studies exclude participants with comorbidities that increase risk for severe COVID-19 Participants in clinical trials will be followed up for at least 1-year after vaccination to assess long-term risk In Arcturus Therapeutics Phase 2 and 3 studies, an independent DSMB will assess the risk of VAERD

Other potential risks of trial participation beyond those associated with study vaccine include risks relating to blood sampling and breach of confidentiality.

Blood sampling may be associated with transient asthenia, risk of fainting, bruising, or infection at the blood sampling site. Risk of infection is reduced by cleansing of the skin prior to blood withdrawal. Risk of fainting is reduced by performing blood sampling with the participant in a seated position.

As study participation involves provision of personal health information by the participant to the site staff, measures are in place to reduce the risk of sharing of this personal information with others. Measures include maintenance of personal information in secure locations (eg,

Arcturus Therapeutics, Inc.
Protocol ARCT-021-04, Version 6.0

ARCT-021
09 March 2022

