7.6.5 Analysis of Exploratory Endpoints

Statistical analyses of exploratory endpoints will be descriptive over time point by vaccine group in the mITT set, unless otherwise specified. These endpoints include the following:

- Descriptive statistics of GMT in cases of confirmed COVID-19, confirmed severe COVID-19, and asymptomatic SARS-CoV-2 infection over time point by the vaccine group.
- CMI responses to SARS-CoV-2 may be measured in a subset of participants. Quantity, phenotype, and percentage of cytokine-producing SARS-CoV-2 spike protein-specific T cells, as measured by flow cytometry/intracellular cytokine staining assay (Days 0, 14, 28, 42, 56, 208, 236, and Early Termination).

Arcturus Therapeutics, Inc.
Protocol ARCT-021-04, Version 6.0

ARCT-021
09 March 2022

- The durability of immune response following vaccination with ARCT-021 versus placebo will be evaluated in binding, neutralizing antibody responses and CMI responses up to Day 236 after first vaccination.

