4.1. Baseline Definition

For both the priming vaccination phase and booster vaccination phase, the baseline is defined as the last non-missing assessment prior to the first priming study vaccine administration. Both scheduled and unscheduled visits and assessments will be used in determining baseline. The change from baseline is calculated as the post-baseline value minus the baseline value.

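### SAP 8.3.2 leaves its Th1/Th2 variable undefined and summarises an apparent quotient by mean, SD and change from baseline, which break down when net Th2 is near zero

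*SAP*

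**What the plan says.** SAP 8.3.2 groups the cell-mediated responses in three sets. The third, "Th1/Th2 CD4+ T-cell responses background subtracted (combined pools"), contains IFN-γ and then "IL-4, IL-4+ IL-13+, IFN- γ + / IL4+ IL13"+. Both parts of the last item also appear on their own. For all the listed responses, "Descriptive statistics (N, mean, SD, min, Q1, median, Q3, max) will be provided for each visit including change from baseline at each timepoint". SAP 4.1 makes the change an arithmetic difference: "The change from baseline is calculated as the post-baseline value minus the baseline value".

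"Box plots will be provided for the following for priming vaccination period (mITT CMI subset"), and the plotted items include IFN-γ, IL4+IL13+, IFN-γ+/IL4+IL13+ and, separately, Th1/Th2.

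The unit comes from Protocol 7.6.5: "Quantity, phenotype, and percentage of cytokine-producing SARS-CoV-2 spike protein-specific T cells".

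Neither document states a log transformation, truncation at zero, a positivity threshold or a rule for a zero or negative denominator. The only low-value rule, in SAP 4.6, sets results below an assay limit to half that limit. The limits listed in SAP 8.2.1, 8.3.1 and 8.3.3 are for antibody and ACE2 assays; none is given for intracellular cytokine staining.

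**The concern.** A background-subtracted response is the stimulated value minus the unstimulated value. When the true Th2 response is close to zero, noise alone puts the net value at or below zero in a sizeable share of samples. Divided into a clearly positive IFN-γ value, it gives a large negative number, an undefined one or a very large positive one. An arithmetic mean and SD of such values say little.

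This setting is foreseeable. Protocol 1.5 reports a Th1-dominant CD4+ response to this vaccine, so a small Th2 denominator is what the sponsor expects. Before vaccination and in placebo recipients both terms are near zero, and the planned change from baseline needs the quotient to exist at Day 0.

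At stake is whether one exploratory table and its box plots can be read. Without a stated rule, zeros and negatives are left to whoever programs the table.

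**Working it through.** The documents give no figure for this variable, so there is none to reproduce. Everything below illustrates with assumed inputs.

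**Assumed, not in the documents.** IFN-γ+ is lognormal across participants, median 0.10%, log-SD 0.8. True net Th2 (IL-4+IL-13+) is fixed at 0.02%, 0.01% or 0.005%. Subtraction noise is normal, SD 0.01%, on both terms. The group size of 25 is the smallest individual booster group in Protocol 7.3; the size of the CMI subset is not stated.

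**Step 1: denominators at or below zero.** P(net Th2 ≤ 0) = Φ(−Th2/SD).
- Th2 0.02%: Φ(−2) = 2.3%
- Th2 0.01%: Φ(−1) = 15.9%
- Th2 0.005%: Φ(−0.5) = 30.9%

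**Step 2: the quotient.** 40,000 simulated samples of 25 per row. The true value is the ratio of medians, 0.10/Th2.

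| Th2 | True quotient | Means negative | Means outside a factor of 2 | Median of quotient |
|---|---|---|---|---|
| 0.02% | 5 | 8% | 44% | 5.2 |
| 0.01% | 10 | 25% | 61% | 7.1 |
| 0.005% | 20 | 38% | 71% | 6.3 |

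The mean is unreliable in every row. The median is adequate at 0.02% and biased low at 0.005%.

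**Step 3: sensitivity to noise.** With the SD halved to 0.005% and Th2 at 0.02%, no mean was negative and about 6% fell outside a factor of 2. What matters is Th2 relative to noise: Th2 0.01% with SD 0.005% behaves like the first row of the table, since both give Φ(−2).

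**Step 4: a different noise model.** Stimulated and background counts were taken as Poisson, with 100,000 CD4+ events and backgrounds of 0.01% (Th2) and 0.02% (Th1), all assumed.
- Th1 0.10%, true Th2 zero: 8.9% of quotients undefined, 45.6% negative, median −6.2.
- Th1 0.10%, Th2 0.005%: 4.9% undefined, 13.4% negative, mean 14.3 against 20.
- Th1 0.10%, Th2 0.02%: practically none undefined or negative, median 5.0 against 5.
- Both truly zero, as at baseline or in placebo: 8.9% undefined, 42.5% negative, and 21.4% positive only because both terms are negative.

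**Step 5: would the half-limit rule rescue it?** For Th1 0.10% and true Th2 zero in the Step 4 model, setting values below 0.005% to 0.0025% gives a mean of 36.2. Setting values below 0.01% to 0.005% gives 19.8. With no floor the mean is 0.0 (SD 52.5). A limit would make every quotient defined, but the answer would then depend on that limit, and the SAP states none for this assay.

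**Step 6: a bounded alternative.** The share max(IFN-γ,0)/[max(IFN-γ,0)+max(IL-4+IL-13,0)], in the Step 2 model without a positivity restriction, has median 0.96 at Th2 0.005%. The true value is 0.10/0.105 = 0.95.

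**The case against.** The SAP does not use the word ratio here. Where it intends one, in SAP 8.3.4, it says so and tabulates numerator and denominator. In SAP 8.3.2 the slash sometimes just joins names, as in CD4+/CD8+. This stands to the extent that the quotient is an inference, although the natural one because both parts are already listed singly. It also shows that the variable needs a definition.

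The components are already summarised separately with medians and quartiles. In the Step 2 model the median IFN-γ exceeded the median IL-4+IL-13+ in practically every sample. A reader might infer that the plan would hide Th1 dominance; it would not, because the component tables still show it.

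A reader might also infer that the trial's VAERD assessment rests on this variable. The documents do not support that. The statement in Protocol Table 1-1, "A Th1-dominant CD4+ response was observed on ICS evaluation of subjects at the interim analysis", concerns the first-in-human study. In this trial, Protocol Table 2-3 and SAP Table 2-3 assign VAERD to unblinded DSMB review of the frequency and severity of COVID-19 cases.

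Nor can one say that the plan drops its most Th1-skewed participants. Failures concentrate in arms and visits where Th2 is low. Within them, chance noise largely decides whose denominator is non-positive, and under a continuous noise model an exact zero does not occur.

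Finally, every input to the size is assumed, and favourable inputs largely remove the problem. That is correct.

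**Conclusion.** The point holds, as a minor one. On the natural reading, SAP 8.3.2 plans a mean, SD and change from baseline for a quotient whose denominator is expected to be near zero, with no rule for zero or negative values and an undefined Th1/Th2 plot variable. Those statistics are not interpretable in that setting, and the median is biased low at the lowest Th2 levels.

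That the problem can arise follows from the definitions; how often depends on the assay. The illustrated range of 2% to 31% non-positive denominators and 8% to 38% negative means rests on the assumed spread, Th2 levels and noise. CMI is exploratory, may be measured in a subset only, and Protocol 7.2 plans no hypothesis tests. No primary or secondary conclusion is affected.

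**What to change.** In SAP 8.3.2:

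- State whether IFN-γ+ / IL4+ IL13+ is a quotient, and define the Th1/Th2 box-plot variable.
- Drop mean, SD and change from baseline for the quotient.
- Report instead the Th1 share from Step 6, with median and IQR, at post-vaccination visits, in participants whose denominator sum exceeds a positivity threshold fixed in advance from the staining assay.
- State per arm how many participants are excluded by the threshold, and how many sit at 1.0 because net Th2 was at or below zero. That ceiling is partly noise and should be visible.
- Read the share beside the component summaries already planned.

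The cost is SAP wording, one derived variable and a threshold from the laboratory. Non-responders, probably including most placebo recipients, leave this one exploratory table; they remain in the component tables.
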